15.3 Safety

15.3.1 Tables

Number	Title	Population	Interim	Programming notes
14.3.1.1.1	Overview of TEAEs	Safety	Y	
14.3.1.1.2	Summary of TEAEs by System Organ Class and Preferred Term	Safety	Y	

Number	Title	Population	Interim	Programming notes
14.3.1.1.3	Summary of Treatment Phase TEAEs by System Organ Class and Preferred Term	Safety		
14.3.1.1.4	Summary of Follow-up Phase TEAEs by System Organ Class and Preferred Term	Safety		
14.3.1.2	Summary of Related TEAEs by System Organ Class and Preferred Term	Safety		
14.3.1.3	Summary of TEAEs of CTCAE Grade 3 or Above by System Organ Class and Preferred Term	Safety	Y	
14.3.1.4	Summary of Non-serious TEAEs Reported by at Least 5% of Participants in Any Treatment Group by System Organ Class and Preferred Term	Safety		
14.3.1.5	Summary of Serious TEAEs by System Organ Class and Preferred Term	Safety	Y	
14.3.1.6	Summary of Fatal TEAEs by System Organ Class and Preferred Term	Safety		
14.3.1.7	Summary of TEAEs Leading to Permanent Discontinuation from Study Drug by System Organ Class and Preferred Term	Safety	Y	
14.3.1.8	Summary of TEAEs Leading to Withdrawal from the Study by System Organ Class and Preferred Term	Safety	Y	
14.3.4.1.1	Summary of Haematology Parameters	Safety		
14.3.4.1.2	Shifts from Baseline to Worst-case Post-Baseline with Respect to the Normal Range for Haematology Parameters	Safety		
14.3.4.1.3	Shifts from Baseline to Worst-case Post-Baseline with Respect to the PCI Criteria for Haematology Parameters	Safety		
14.3.4.2.1	Summary of Chemistry Parameters	Safety		
14.3.4.2.2	Shifts from Baseline to Worst-case Post-Baseline with Respect to the Normal Range for Chemistry Parameters	Safety		
14.3.4.2.3	Shifts from Baseline to Worst-case Post-Baseline with Respect to the PCI Criteria for Chemistry Parameters	Safety		
14.3.5.1	Summary of ECG Parameters	Safety		

Number	Title	Population	Interim	Programming notes
14.3.5.2	Shifts from Baseline to Worst-case Post-Baseline with Respect to the PCI Criterion for QTcF	Safety		
14.3.6.1	Summary of Vital Signs	Safety		
14.3.6.2	Shifts from Baseline to Worst-case Post-Baseline with Respect to the PCI Criterion for Vital Signs	Safety		

15.4 Data Listings

Number	Title	Population	Interim	Programming notes
16.2.1.1	Inclusion/Exclusion criteria failed	Enrolled		
16.2.1.2	End of Treatment Disposition	miITT		
16.2.1.3	End of Part A Disposition	miITT		
16.2.1.4	Participants for Whom the Blind Was Broken	miITT		
16.2.1.5	Planned and Actual Treatments	miITT		
16.2.1.6	Visits Missed Due to COVID-19	miITT		
16.2.2	Protocol Deviations	miITT		
16.2.3	Participants Excluded from Any Population	Enrolled		
16.2.4.1	Demographics	miITT		
16.2.4.2	Baseline Disease Characteristics	miITT		
16.2.4.3	Past and Current Psoriasis Treatment	miITT		
16.2.4.4	Medical History	miITT		
16.2.4.5	Prior Medications	miITT		
16.2.4.6	Concomitant Medications	miITT		
16.2.5.1	Exposure to Study Drug	miITT		
16.2.5.2	Study Drug Compliance	miITT		
16.2.6.1	Individual Components of the PASI Questionnaire	miITT		
16.2.6.2	PASI Endpoints	miITT		
16.2.6.3	Time to Event Endpoints for PASI	miITT		

Number	Title	Population	Interim	Programming notes
16.2.6.4	PGA Score	miITT		
16.2.6.5	BSA and PGA*BSA	miITT		
16.2.6.6	LSS Items and Score	miITT		
16.2.6.7	DLQI Items and Score	miITT		
16.2.6.8	mNAPSI Items and Score	miITT		
16.2.6.9	PSI Items and Total Score	miITT		
16.2.6.10	SF-36 Pain Score: Individual Items and Scores	miITT		
16.2.6.11	SF-36 Vitality Score: Individual Items and Scores	miITT		
16.2.6.12	Pain and Fatigue VAS Scores	miITT		
16.2.7.1.1	Adverse Events	Enrolled		
16.2.7.1.2	Serious Adverse Events	Enrolled		
16.2.7.1.3	Fatal Adverse Events	Safety		
16.2.7.1.4	Adverse Events Leading to Permanent Discontinuation from Study Drug	Safety		
16.2.7.2.1	Haematology Parameters	Safety		
16.2.7.2.2	Haematology Parameters for Participants with at Least One PCI Value	Safety		
16.2.7.2.3	Clinical Chemistry Parameters	Safety		
16.2.7.2.4	Clinical Chemistry Parameters for Participants with at Least One PCI Value	Safety		
16.2.7.2.5	Urinalysis Parameters	Safety		
16.2.7.3.1	ECG Parameters	Safety		
16.2.7.3.2	ECG Parameters for Participants with at Least One PCI Value	Safety		
16.2.7.4.1	Vitals Signs	Safety		
16.2.7.4.2	Vitals Signs for Participants with at Least One PCI Value	Safety		
16.2.7.5	Physical Examination	Safety		
16.2.7.6	Female Fertility Status and Pregnancy Test Results	Safety		
16.2.7.7	Bristol Stool Scale	Safety		

15.5 Part B Outputs

15.5.1 Tables

Number	Title	Population	Programming notes
14.4.1.1	Summary of Disposition in Part B	Part B	
14.4.1.2	Summary of Attendance at Each Visit in Part B	Part B	
14.4.1.3	Summary of Missed Visits Due to COVID-19 in Part B	Part B	
14.4.1.4	Summary of Populations	Part B	
14.4.1.5	Summary of Demography	Part B	
14.4.1.6	Summary of Baseline Disease Characteristics	Part B	
14.4.1.7	Summary of Concomitant Medications Used in Part B	Part B	
14.4.2.1	Summary of Percentage Change from Baseline in PASI Score	Part B	
14.4.2.2	Summary of Change from Baseline in PASI Score	Part B	
14.4.2.3	Summary of Percentage Change from Baseline in PGA*BSA	Part B	
14.4.2.4	Summary of Change from Baseline in PGA*BSA	Part B	
14.4.2.5	Summary of Percentage Change from Baseline in LSS	Part B	
14.4.2.6	Summary of Change from Baseline in LSS	Part B	
14.4.2.7.1	Summary of Percentage Change from Baseline in DLQI Score - Main Analysis	Part B	
14.4.2.7.2	Summary of Percentage Change from Baseline in DLQI Score – Sensitivity Analysis	Part B	
14.4.2.8.1	Summary of Change from Baseline in DLQI Score - Main Analysis	Part B	
14.4.2.8.2	Summary of Change from Baseline in DLQI Score - Sensitivity Analysis	Part B	
14.4.2.9	Summary of Percentage Change from Baseline in mNAPSI Total Score for Participants with Psoriatic Nail Involvement at Baseline	Part B	
14.4.2.10	Summary of Change from Baseline in mNAPSI Total Score for Participants with Psoriatic Nail Involvement at Baseline	Part B	
14.4.2.11	Summary of Percentage Change from Baseline in PSI Total Score	Part B	

Number	Title	Population	Programming notes
14.4.2.12	Summary of Change from Baseline in PSI Total Score	Part B	
14.4.2.13	Summary of Percentage Change from Baseline in PSI Itch Score	Part B	
14.4.2.14	Summary of Change from Baseline in PSI Itch Score	Part B	
14.4.2.15	Cumulative Incidence of Partial Relapse	Week 16 Responders	
14.2.2.16	Cumulative Incidence of Relapse	Week 16 Responders	
14.4.2.17	Cumulative Incidence of Rebound	miITT	
14.4.2.18	Summary of Duration of Remission	miITT	
14.2.2.20	Summary of Duration of Treatment Success	miITT	
14.4.2.21	Summary of Duration of Therapeutic Effect	miITT	
14.4.3.1	Overview of Related TEAEs Starting in Part B	Part B	
14.4.3.2	Summary of Related TEAEs by System Organ Class and Preferred Term Starting in Part B	Part B	

15.5.2 Figures

Number	Title	Population	Programming notes
14.4.2.1	Mean (+/-SD) Percentage Change in PASI Score Over Time	Part B	
14.4.2.2	Mean (+/-SD) Change in PASI Score Over Time	Part B	
14.4.2.3	Mean (+/-SD) Percentage Change in PGA*BSA Over Time	Part B	
14.4.2.4	Mean (+/-SD) Change in PGA*BSA Over Time	Part B	
14.4.2.5	Mean (+/-SD) Percentage Change in LSS Over Time	Part B	
14.4.2.6	Mean (+/-SD) Change in LSS Over Time	Part B	
14.4.2.7.1	Mean (+/-SD) Percentage Change in DLQI Score Over Time – Main Analysis	Part B	
14.4.2.7.2	Mean (+/-SD) Percentage Change in DLQI Score Over Time – Sensitivity Analysis	Part B	

Number	Title	Population	Programming notes
14.2.2.8.1	Mean (+/-SD) Change in DLQI Score Over Time – Main Analysis	Part B	
14.2.2.8.2	Mean (+/-SD) Change in DLQI Score Over Time – Sensitivity Analysis	Part B	
14.4.2.9	Mean (+/-SD) Percentage Change in mNAPSI Total Score Over Time for Participants with Psoriatic Nail Involvement at Baseline	Part B	
14.4.2.10	Mean (+/-SD) Change in mNAPSI Total Score Over Time for Participants with Psoriatic Nail Involvement at Baseline	Part B	
14.4.2.11	Mean (+/-SD) Percentage Change in PSI Total Score Over Time	Part B	
14.4.2.12	Mean (+/-SD) Change in PSI Total Score Over Time	Part B	
14.4.2.13	Mean (+/-SD) Percentage Change in PSI Itch Score Over Time	Part B	
14.4.2.14	Mean (+/-SD) Change in PSI Itch Score Over Time	Part B	
14.4.2.15	Cumulative Incidence (+/- 95% CI) of Partial Relapse	Week 16 Responders	
14.4.2.16	Cumulative Incidence (+/- 95% CI) of Relapse	Week 16 Responders	
14.4.2.17	Cumulative Incidence (+/- 95% CI) of Rebound	miITT	

15.5.3 Data Listings

Number	Title	Population	Programming notes
16.2.8.1.1	Reasons for Withdrawal from Part B	Part B	
16.2.8.1.2	Visits Missed Due to COVID-19 in Part B	Part B	
16.2.8.1.3	Concomitant Medications Started or Changed in Part B	Part B	
16.2.8.2.1	Individual Components of the PASI Questionnaire – Part B Visits	Part B	
16.2.8.2.2	PASI Endpoints– Part B Visits	Part B	
16.2.8.2.4	PGA Score– Part B Visits	Part B	
16.2.8.2.5	BSA and PGA*BSA – Part B Visits	Part B	
16.2.8.2.6	LSS Items and Score– Part B Visits	Part B	
16.2.8.2.7	DLQI Items and Score – Part B Visits	Part B	

Number	Title	Population	Programming notes
16.2.8.2.8	mNAPSI Items and Score – Part B Visits	Part B	
16.2.8.2.9	PSI Items and Total Score – Part B Visits	Part B	
16.2.8.3	Adverse Events Started or Changed in Part B	Part B	

16 Appendix 2: Psoriasis Area and Severity Index Score

Intensity

A representative area of psoriasis is selected for each body region (head and neck, upper limbs, trunk, lower limbs).

The intensity of erythema (redness), induration (thickness) and desquamation (scaling) of the psoriasis in each body region is scored as:

- 0 = None
- 1 = Mild
- 2 = Moderate
- 3 = Severe
- 4 = Very Severe

An intensity score is calculated for each body region as the sum of the three scores for erythema, induration and desquamation.

- A1 = Intensity score for head and neck
- A2 = Intensity score for upper limbs
- A3 = Intensity score for trunk
- A4 = Intensity score for lower limbs

Each subtotal is multiplied by the body surface area represented by that region as follows:

- B1 = 0.1 x A1
- B2 = 0.2 x A2
- B3 = 0.3 x A3
- B4 = 0.4 x A4

Percentage area affected

The percentage area affected by psoriasis is evaluated in each of the four body regions. In each body region the area is expressed as:

- 0 = not affected at all
- 1 = >0% - <10%
- 2 = 10% - <30%
- 3 = 30% - <50%
- 4 = 50% - <70%
- 5 = 70% - <90%
- 6 = 90% - 100%

PASI score calculation

Each of the body area scores is multiplied by the intensity score for the relevant body region (B1-B4) to gives four area and intensity scores (C1-C4).

The PASI score is the sum of the four area and intensity scores:

$$\text{PASI score} = C1 + C2 + C3 + C4.$$

17 Appendix 3: Physician Global Assessment

The physician will give a score on the participant's psoriasis disease activity, according to the following grades:

Induration (I) (averaged over all lesions; use the National Psoriasis Foundation Reference card for measurement)

- 0 = no evidence of plaque elevation
- 1 = minimal plaque elevation, =0.25mm
- 2 = mild plaque elevation, =0.5mm
- 3 = moderate plaque elevation, =0.75mm
- 4 = marked plaque elevation, =1mm
- 5 = severe plaque elevation, =1.25mm or more

Erythema (E) (averaged over all lesions)

- 0 = no evidence of erythema, hyperpigmentation may be present
- 1 = faint erythema
- 2 = light red coloration
- 3 = moderate red coloration
- 4 = bright red coloration
- 5 = dusky to deep red coloration

Scaling (S) (averaged over all lesions)

- 0 = no evidence of scaling
- 1 = minimal; occasional fine scale over less than 5% of the lesion
- 2 = mild, fine scale dominates
- 3 = moderate, course scale dominates
- 4 = marked, thick nontenacious scale dominates
- 5 = severe, very thick nontenacious scale dominates

The PGA score will be the average of the three scores and will be rounded to the nearest whole number.

18 Appendix 4: Dermatology Quality of Life Index

The DLQI consists of 10 questions:

1. Over the last week, how itchy, sore, painful or stinging has your skin been?
2. Over the last week, how embarrassed or self-conscious have you been because of your skin?
3. Over the last week, how much has your skin interfered with you going shopping or looking after your home or garden?
4. Over the last week, how much has your skin influenced the clothes you wear?
5. Over the last week, how much has your skin affected any social or leisure activities?
6. Over the last week, how much has your skin made it difficult for you to do any sport?
7. Over the last week, has your skin prevented you from working or studying?
If "No", over the last week how much has your skin been a problem at work or studying?
8. Over the last week, how much has your skin created problems for your partner or any of your close friends or relatives?
9. Over the last week, how much has your skin caused any sexual difficulties?
10. Over the last week, how much of a problem has the treatment for your skin been, for example by making your home messy, or taking up time?

Questions 1 and 2 is scored on a four-point Likert scale:

- 3 = Very much
- 2 = A lot
- 1 = A little
- 0 = Not at all

Questions 3-6 and 8-10 also have an option of not relevant and are scored as:

- 3 = Very much
- 2 = A lot
- 1 = A little
- 0 = Not at all
- 0 = Not relevant

Question 7 is a 2-part question and is scored as:

- 3 = Yes
- 3 = No; Very much
- 2 = No; A lot
- 1 = No; A little
- 0 = No; Not at all
- 0 = Not relevant

Any unanswered question is scored as 0.

The DLQI score is the sum of the 10 item scores.

19 Appendix 5: Modified Nail Psoriasis Severity Index

The mNAPSI assesses each nail abnormality for each of the participant's 10 fingernails. If the rater is unsure which grade to give they should select the lower of the grades.

Three features or groups of features (pitting, onycholysis and oil-drop dyschromia, and crumbling) of each fingernail will be graded on a scale from zero to 3, according to the directions below. Four features (leukonychia, splinter haemorrhages, hyperkeratosis, and red spots in the lunula) will be graded as either present or absent for each fingernail.

Onycholysis and oil-drop dyschromia

Onycholysis: Separation of the nail plate from the nail bed. The separated part of the nail is opaque and can have white, yellow, or greenish tinge. If there is a piece of nail missing, estimate where the nail normally would have ended at the end of the nail bed, and count that missing part as involved in onycholysis.

Oil-drop (salmon patch) dyschromia: Reddish-brown discoloration under the nail plate.

Onycholysis and oil-drop dyschromia are considered together. When looking at the nail, combine the total percentage area of the nail that is affected by either and use that combined total to score the nail.

Score: Percent of nail with onycholysis or oil-drop dyschromia present

- 0 = No onycholysis or oil drop dyschromia present
- 1 = 1–10% of the nail has onycholysis or oil-drop dyschromia
- 2 = 11–30% of the nail has onycholysis or oil-drop dyschromia
- 3 = > 30% of the nail has onycholysis or oil-drop dyschromia

Pitting

Small, sharply defined depressions in the nail surface. Pits are discrete abnormalities ("ice-pick-like"). If there is nail plate crumbling that is confluent with pits, do not score for pits. If the pits are separate from crumbling, they may be scored regardless of whether crumbling is present or not.

Score: Number of pits

- 0 = 0
- 1 = 1–10
- 2 = 11–49
- 3 = > 50

Nail plate crumbling

Crumbling or fragmentation of friable nail plate which may be associated with confluent pitting. Crumbling involves alteration of the nail plate surface. Horizontal ridging of the nail, "wave-like" appearance, and horizontal lines are all features of crumbling.

Score: Percent of nail with crumbling present

- 0 = No crumbling
- 1 = 1–25% of the nail has crumbling
- 2 = 26–50% of the nail has crumbling
- 3 = > 50% of the nail has crumbling

Additional features

The next 4 abnormalities are scored only by their presence or absence. A score of 1 indicates present and a score of zero indicates not present.

- Leukonychia: White spots in the nail plate due to psoriasis in the mid matrix. Leukonychia are just color changes. If it appears that there is depression or irregularity to the nail surface, this may be pitting or crumbling, not leukonychia. If the leukonychia is adjacent to, or confluent with crumbling or pits, it is counted as part of the crumbling or pitting and not as a separate abnormality.
- Splinter hemorrhages: Small, longitudinal, linear, dark brown haemorrhage under the fingernail.
- Nail bed hyperkeratosis: Thickened keratin in the nail bed.
- Red spots in the lunula: Small pink or red macules in the lunula.

mNAPSI score

Each fingernail is scored as above to give a score of 0-13. The mNAPSI score is the total of the 10 individual fingernail scores.

20 Appendix 6: Psoriasis Symptom Inventory

The PSI is a patient reported outcome which assesses 8 symptoms of severity with a recall period of 24 hours. It will be completed daily by participants in the 7 days before attending the site for a visit.

The participant should answer each of the following questions every day:

Overall, during the last 24 hours:

- How severe was the itch from your psoriasis?
- How severe was the redness from your lesions?
- How severe was the scaling from your lesions?
- How severe was the burning from your lesions?
- How severe was the stinging from your lesions?
- How severe was the cracking from your lesions?
- How severe was the flaking from your lesions?
- How severe was the pain from your lesions?

Each question is scored on a 5-point scale as follows:

- 0 = Not at all
- 1 = Mild
- 2 = Moderate
- 3 = Severe
- 4 = Very Severe

If the participant has answered the symptom question on at least 5 of the 7 days, a weekly symptom score will be calculated as the average of the available daily scores for each symptom. If less than 5 daily answers are provided, the weekly symptom score will be considered as missing.

The PSI total score will be the sum of the 8 weekly symptom scores. It will only be calculated when all 8 weekly symptom scores are non-missing.

21 Appendix 7: SF-36 Pain and Vitality Scores

Pain score

The pain score will be calculated from questions 21 and 22 of the SF-36 questionnaire:

Q21: How much bodily pain have you had during the past 4 weeks?

- 1 = None
- 2 = Very mild
- 3 = Mild
- 4 = Moderate
- 5 = Severe
- 6 = Very severe

The Q21 score = $100 * [(6-x)/5]$ where x=1-6 is the Q21 item value as above.

Q22: During the past 4 weeks, how much did pain interfere with your normal work (including both work outside the home and housework)?

- 1 = Not at all
- 2 = A little bit
- 3 = Moderately
- 4 = Quite a bit
- 5 = Extremely

The Q22 score = $100 * [(5-x)/4]$ where x=1-5 is the Q22 item value as above.

The SF-36 bodily pain score is the average of the Q21 and Q22 scores. If at least one of the two questions have been answered, the SF-36 bodily pain score will be calculated.

Vitality score

The vitality score will be calculated from questions 23, 27, 29 and 31 of the SF-36 questionnaire:

How much of the time during the past 4 weeks...

Q23: Did you feel full of pep?

Q27: Did you have a lot of energy?

Q29: Did you feel worn out?

Q31: Did you feel tired?

Each question has possible answers (x):

- 1 = All of the time
- 2 = Most of the time
- 3 = A good bit of the time
- 4 = Some of the time
- 5 = A little of the time
- 6 = None of the time

The Q23 score = $100*[(6-x)/5]$ where x=1-6 is the Q23 item value as above.
The Q27 score = $100*[(6-x)/5]$ where x=1-6 is the Q27 item value as above.
The Q29 score = $100*[x/5]$ where x=1-6 is the Q29 item value as above.
The Q31 score = $100*[x/5]$ where x=1-6 is the Q31 item value as above.

The SF-36 vitality score is the average of the Q23, Q27, Q29 and Q31 scores. If at least two of the four questions have been answered, the SF-36 bodily pain score will be calculated.

22 Appendix 8: MedDRA Internationally Agreed Order for System Organ Class

The internationally agreed SOC order to be used for medical history and AE summary tables is provided in [Table 9](#).

Table 9 MedDRA Internationally Agreed SOC Order

Order Number	System Organ Class
1	Infections and infestations
2	Neoplasms benign, malignant and unspecified (incl cysts and polyps)
3	Blood and lymphatic system disorders
4	Immune system disorders
5	Endocrine disorders
6	Metabolism and nutrition disorders
7	Psychiatric disorders
8	Nervous system disorders
9	Eye disorders
10	Ear and labyrinth disorders
11	Cardiac disorders
12	Vascular disorders
13	Respiratory, thoracic and mediastinal disorders
14	Gastrointestinal disorders
15	Hepatobiliary disorders
16	Skin and subcutaneous tissue disorders
17	Musculoskeletal and connective tissue disorders
18	Renal and urinary disorders
19	Pregnancy, puerperium and perinatal conditions
20	Reproductive system and breast disorders
21	Congenital, familial and genetic disorders
22	General disorders and administration site conditions
23	Investigations
24	Injury, poisoning and procedural complications
25	Surgical and medical procedures
26	Social circumstances
27	Product issues

23 Appendix 9: Safety Laboratory Evaluations

Table 10 Safety Laboratory Parameters and Units

Category	Parameter	Conventional Unit	SI Units	PCI Criteria (SI units)	
				Low	High
Hematology	Hemoglobin	g/dL	g/L	<100 ≥20 decrease from BL	>20 increase from BL
	Hematocrit	%	L/L		
	Red blood cell count	10 ⁶ /uL	10 ¹² /L		
	White blood cell count	10 ³ /uL	10 ⁹ /L	<3	
	Platelets	10 ³ /uL	10 ⁹ /L	<75	
	Mean corpuscular volume	fL	fL		
	Mean corpuscular hemoglobin	pg	pg		
	Mean corpuscular hemoglobin concentration	g/dL	g/L		
	Absolute neutrophils	10 ³ /uL	10 ⁹ /L	<1.5	
	Absolute lymphocytes	10 ³ /uL	10 ⁹ /L	<0.8	>4
	Absolute monocytes	10 ³ /uL	10 ⁹ /L		
	Absolute eosinophils	10 ³ /uL	10 ⁹ /L		
	Relative neutrophils	%	%		
	Relative lymphocytes	%	%		
	Relative monocytes	%	%		
	Relative eosinophils	%	%		
	Relative reticulocytes	%	%		

Category	Parameter	Conventional Unit	SI Units	PCI Criteria (SI units)	
				Low	High
Chemistry	Aspartate aminotransferase	U/L	U/L		>3xULN if BL did not exceed ULN, >3xBL if BL was above ULN
	Alanine aminotransferase	U/L	U/L		>3xULN if BL did not exceed ULN, >3xBL if BL was above ULN
	Creatinine	mg/dL	μmol/L		>1.5xULN if did not exceed ULN, >1.5xBL if BL was above ULN
	Potassium	mEq/L	mmol/L		>5.5
	Sodium	mEq/L	mmol/L	<125	>150
	Blood urea nitrogen	mg/dL	mmol/L		
	Total bilirubin	mg/dL	μmol/L		>1.5xULN if BL did not exceed ULN, >1.5xBL if BL was above ULN
	Direct bilirubin	mg/dL	μmol/L		
	CRP	mg/L	nmol/L		
	Creatinine kinase	U/L	U/L		>2.5xULN
	Fasting glucose	mg/dL	mmol/L	<0.17	
	Total cholesterol	mg/dL	mmol/L		>7.77
	HDL cholesterol	mg/dL	mmol/L		
	LDL cholesterol	mg/dL	mmol/L		
	Triglycerides	mg/dL	mmol/L		>3.39

Category	Parameter	Conventional Unit	SI Units	PCI Criteria (SI units)	
				Low	High
Urinalysis	Protein	mg/dL	mg/dL		
	Blood				
	Glucose	mg/dL	mg/dL		
	Ketones	mg/dL	mg/dL		
	Bilirubin				
	pH	pH	pH		
	Nitrites				
	Specific gravity				

BL=Baseline, PCI = potentially clinically important, ULN = Upper limit of normal range.

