10.5 Clinical Laboratory Evaluations

Central laboratory data will be used for all safety laboratory evaluations. [Table 10 \(Section 23\)](#) shows the parameters which will be collected and the units in which they will be supplied. Lab data will be transformed as appropriate to the International System of Units (SI units) as part of the SDTM programming and SI units will be used for all summaries.

Haematology and chemistry parameters will be summarised by visit, including change from baseline for all post-baseline visits.

The number and percentage of participants showing shifts from baseline to worst-case post-baseline with respect to the normal ranges will also be summarised for each haematology and chemistry parameter. Categories will be:

- Low
- Normal
- High

Haematology and chemistry values will also be flagged for potentially clinically important (PCI) values if they meet any of the criteria for Grade 2 or higher events according to CTCAE V5.0. The PCI criteria are listed in [Table 10 \(Section 23\)](#). The number and percentage of participants showing shifts from baseline to worst-case baseline with respect to PCI criteria will be summarised for all parameters where PCI criteria have been defined. Categories will be:

- Low
- Within range
- High

For both the normal range and PCI summaries, the determination of worst-case post-baseline will consider both scheduled and unscheduled assessments which occur after the first dose of study

treatment. Percentages will use the number of participants with at least one post-baseline assessment available as the denominator. If the baseline value is missing it will be assumed to be normal/within range. Worst-case can be either High or Low and if a participant has post-baseline values both above and below the normal range/PCI criteria then they will be counted in both relevant categories.

Haematology and chemistry data will be listed, including changes from baseline, normal ranges, flags for measurements outside the normal range, and flags for meeting PCI criteria. In addition, for participants who meet at least one PCI criteria, all values within the laboratory type (haematology or chemistry) will be listed separately.

Urinalysis data will be listed only.

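### The only fasting-glucose PCI limit in SAP Table 10, below 0.17 mmol/L (about 3.1 mg/dL), is so low that the low-glucose flag will in practice never fire

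*SAP*

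**What the plan says.** SAP Section 10.5 states that haematology and chemistry values will be "flagged for potentially clinically important (PCI) values if they meet any of the criteria for Grade 2 or higher events according to CTCAE V5.0", and it names Table 10 as the list of criteria. On units it says that "SI units will be used for all summaries". Table 10 agrees: the heading over its limit columns begins "PCI Criteria (SI units". The glucose row is "Fasting glucose mg/dL mmol/L <0.17", with the figure in the Low column and nothing in the High column. No other place in the protocol or SAP gives or corrects a glucose limit.

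Two outputs use these limits:

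- Table 14.3.4.2.3, "Shifts from Baseline to Worst-case Post-Baseline with Respect to the PCI Criteria for Chemistry Parameters", covers every parameter that has a PCI criterion. For its denominator, "Percentages will use the number of participants with at least one post-baseline assessment available as the denominator".
- Listing 16.2.7.2.4, "Clinical Chemistry Parameters for Participants with at Least One PCI Value", follows from the rule in Section 10.5 that "for participants who meet at least one PCI criteria, all values within the laboratory type (haematology or chemistry) will be listed separately".

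**The concern.** A limit of 0.17 mmol/L is close to no glucose at all. A threshold meant to pick out Grade 2 or worse low glucose cannot sit there, so the cell conflicts with the rule in Section 10.5 that it is supposed to implement.

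The form of the error matters. A blank cell would tell the reader that no criterion was set. Because a criterion is printed, glucose gets a row in the PCI shift table, and that row will show zero Low in every treatment group. A reader would take that as evidence that no important low values occurred, when the result was fixed in advance by the threshold. Safety is part of the primary objective (Protocol Section 2.1, SAP Section 4.1), and fasting glucose is measured on purpose, at baseline and Weeks 8 and 16 (Protocol Table 6-1).

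**Working it through.** **Inputs**

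- Fasting-glucose Low limit: 0.17 mmol/L (SAP Table 10).
- Total cholesterol High limit: 7.77 mmol/L; triglycerides High limit: 3.39 mmol/L (same table).
- Expected participants with data through Week 16: 42 active and 21 placebo in each of 3 cohorts; 225 randomised (SAP Section 6).
- Conversion factors (standard, not in the documents): glucose mg/dL = mmol/L x 18.016 (molar mass 180.16 g/mol); mg/dL to mmol/L, x 0.0259 for cholesterol and x 0.0113 for triglycerides.

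The documents give no inputs from which 0.17 could be derived, so there is no calculation of the plan's to reproduce. The check is one of units.

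**1. The limit in conventional units**

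0.17 x 18.016 = 3.06 mg/dL. Allowing for rounding of the printed figure (0.165 to 0.175), the range is 2.97 to 3.15 mg/dL.

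**2. Could the figure be in another unit?**

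| Reading of 0.17 | mg/dL | mmol/L |
|---|---|---|
| mmol/L (as headed) | 3.06 | 0.17 |
| mg/dL | 0.17 | 0.009 |
| g/L | 17 | 0.94 |
| g/dL | 170 | 9.4 |

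The first three are all implausibly low, and the last is not a low value. No reading gives a sensible low-glucose limit.

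**3. Is the whole column off?**

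300 x 0.0259 = 7.77 and 300 x 0.0113 = 3.39. The two nearby lipid limits are exactly 300 mg/dL expressed in mmol/L. The column is in SI units as headed, and glucose is the outlier.

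**4. Distance from a plausible limit**

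The documents do not quote the CTCAE cut-off. Assume it lies somewhere between 40 and 70 mg/dL:

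- 40 / 18.016 = 2.22 mmol/L; 2.22 / 0.17 = 13.1
- 70 / 18.016 = 3.89 mmol/L; 3.89 / 0.17 = 22.9

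**5. Effect on the table**

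The denominator is participants with at least one post-baseline sample: 3 x (42 + 21) = 189 if only those expected to provide data through Week 16 count, and 225 if everyone is sampled. A Week 8 sample is enough, so the true figure should be at or above the lower end; replacement participants could add a few. The Low count is 0 throughout.

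**6. A possible cause (inference only)**

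3.0 / 18.016 = 0.1665, which rounds to 0.17. The figure is what would result if a limit already in mmol/L had been converted from mg/dL a second time. Nothing in the documents confirms this, and the finding does not depend on it.

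**The case against.** The strongest reply is that little is lost. Low glucose would still appear in the by-visit summaries (Tables 14.3.4.2.1 and 14.2.30), in the worst-case shifts against the normal range (Table 14.3.4.2.2) and in the full chemistry listing (16.2.7.2.3). Abnormal laboratory results are also to be recorded as adverse events (Protocol Section 6.4), graded by CTCAE v5.0 (Protocol Section 6.2.1.2.1), and events of Grade 2 or above are counted in the overview of treatment-emergent events (SAP Section 10.2). The halting criteria in Protocol Section 11.3.1 do not use the PCI flag, and Table 14.3.4.2.3 is not among the interim outputs.

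All of that is correct, and it limits the consequence. It does not repair the cell. The adverse-event route depends on the investigator recording the event, whereas the PCI flag is meant to work from the laboratory value alone. The normal-range table shows that a value was low but not whether it reached the chosen grade.

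It is also fair to say that the 13-to-23-fold figure depends on an assumed range, that the double-conversion explanation is conjecture, and that a count of zero says nothing more for having a denominator attached. The finding needs only two things: 0.17 mmol/L is about 3 mg/dL, and Section 10.5 calls for a Grade 2 limit.

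**Conclusion.** The concern holds. The fasting-glucose limit in Table 10 is wrong as written and does not implement the rule in Section 10.5. The low-glucose category in Table 14.3.4.2.3 would be 0 of roughly 189 to 225 participants whatever the true rate, and glucose could never be the reason a participant enters Listing 16.2.7.2.4. Other chemistry parameters can still populate both outputs.

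This rests on one premise from general physiology, not from the documents: a valid fasting sample from a trial outpatient will not be near 3 mg/dL. The size of the discrepancy also depends on the assumed range for the CTCAE limit. The efficacy analyses and the sample size are unaffected. It should be corrected, because it is a misleading entry in a prespecified safety output and is cheap to put right.

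**What to change.** Check the glucose Low cell in SAP Table 10 against the CTCAE v5.0 Grade 2 low-glucose criterion that Section 10.5 already adopts, and enter that limit once, in mmol/L. Then program Table 14.3.4.2.3 and Listing 16.2.7.2.4 from the corrected value, or re-run them if they already exist. The cost is one table cell and one run of those two outputs; no new data are needed.
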